## 5.10.2 Dosing Delays and Modifications

## 5.10.2.1 Missed Doses

Patients will be encouraged to stay on schedule even if a dose is missed. Dosing will be tracked in the patients' diaries. Lack of compliance with the study protocol may result in removal from the study. This will be decided on an individual basis by the investigators.

Myalgias and arthralgias are known to be associated with PF-04449913, and may be more significant in the post HSCT setting. For patients with  $\geq$  grade 3 myalgias or arthralgias, dose interruption will occur until the symptoms resolve to  $\leq$ grade 1. If this does not occur after an interruption of 28 days the patient will come off of the study. If it does occur within 28 days of interruption, resumption of PF-04449913 will occur at the 100 mg dose, but after re-introduction the drug will be given for 21 days consecutively with 7 days off each cycle. If a subsequent  $\geq$  grade 3 myalgia or arthralgia event occurs, dose interruption will occur until the symptoms resolve to  $\leq$ grade 1. If this does not occur after an interruption of 28 days the patient will come off of the study. If it does occur within 28 days of interruption, resumption of PF-04449913 will occur at the 50 mg dose, again administered 21 days on and 7 days off. Another  $\geq$  grade 3 myalgia or arthralgia event will result in the same interruption and resumption schedule as above, this time with a dose reduction to 25 mg, and an additional  $\geq$  grade 3 myalgia or arthralgia event will result in termination of the study.

Other toxicities will be managed as follows:

Toxicity						
Grade 1 or 2	Grade 3	Grade 4				
Continue at current dose	Withhold until toxicity returns to ≤ grade 1 for related or possibly related non hematologic toxicities then resume the same dose level or reduce by 50%, at the discretion of the investigator (nausea, vomiting or diarrhea must persist at grade 3 or 4 despite maximal medical therapy to require a dose reduction). One additional 50% dose reduction is permitted for a second episode. At the discretion of the investigator, dose re- escalation by 100% increments to full dose may be attempted if AEs remain resolved after dose reduction (s).	Withhold until toxicity returns to ≤ grade 1 for related or possibly related non hematologic toxicities and ≤ grade 3 for related or possibly related hematologic toxicities, then reduce by 50% or discontinue treatment, at the discretion of the investigator (nausea, vomiting or diarrhea must persist at grade 3 or 4 despite maximal medical therapy to require a dose reduction). One additional 50% dose reduction is permitted for a second episode. At the discretion of the investigator, dose re-escalation by 100% increments to full dose may be attempted if AEs remain resolved after dose reduction (s).				

Recommended Dose Modifications for Treatment-Related QTcF	
Prolongation	

QTcF Prolongation					
		Grade			
1	2	3	4		
• No change	
 
Withhold study treatment
 
Assess for and correct electrolyte abnormalities.
 
Withhold any concomitant medications that may cause QTcF prolongation.
 
Resume study treatment at prior dose if QTcF returns to ≤470 msec and to within 20 msec of baseline <7 days. β
 
Resume study treatment at one lower dose level if QTcF returns to ≤470 msec and to within 20 msec of baseline between 7-14 days, or if a prior dosing interruption for QTcF prolongation has occurred. β
 
	
 
Withhold study treatment
 
Assess for and correct electrolyte abnormalities.
 
Withhold any concomitant medications that may cause QTcF prolongation.
 
Resume study treatment at prior dose if QTcF returns to ≤470 msec and to within 20 msec of baseline <7 days. β
 
Resume study treatment at one lower dose level if QTcF returns to ≤470 msec and to within 20 msec of baseline between 7-14 days, or if a prior dosing interruption for QTcF prolongation has occurred. β
 
	• Discontinue study treatment permanently		
	
 
Discontinue study treatment permanently if:
 
The QTcF prolongation does not return to ≤470 ms within 14 days.
 
≥ Grade 2 QTcF prolongation recurs after one dose reduction.
 
If anytime during the 14- day window, the patient has a confirmed mean QTcF interval >515 ms or becomes symptomatic.
 
	
 
Discontinue study treatment permanently if:
 
The QTcF prolongation does not return to ≤470 ms within 14 days.
 
≥ Grade 2 QTcF prolongation recurs after one dose reduction.
 
If anytime during the 14- day window, the patient has a confirmed mean QTcF interval >515 ms or becomes symptomatic.
 
			
QTcF = Fi	idericia's QT correction, ms = mi	lliseconds			
	should be repeated approximate ruption for QTcF prolongation.	ely 7 days after study treatment r	esumption following		

## 5.10.3 Data and Safety Monitoring

AEs and SAEs will be reviewed on an ongoing basis to identify safety concerns, and the investigators may discontinue the study if excessive toxicity is observed. In addition, the study will be monitored by the Cancer Center's data safety and monitoring committee (DSMC) at times designated by the committee.

## Oversight and Monitoring

The Principal Investigator will be responsible for monitoring the safety and efficacy of the trial, executing the DSM plan, and complying with all reporting requirements to local and federal authorities. This will be accomplished under the oversight of the Data & Safety Monitoring Committee (DSMC) of the University of Colorado Cancer Center (UCCC). The DSMC is responsible for monitoring data quality and patient safety for all clinical studies at UCCC. A summary of the DSMC activities follows:

- Conduct of internal audits
- Ongoing review of all reportable adverse events and all serious/unanticipated adverse events
- Supervises internal DSM boards and/or performs as an internal DSMB
- Has the authority to close and/or suspend trials for safety or trial conduct issues and may submit recommendations for corrective actions to the Associate Directors Executive Committee
- Performs routine internal monitoring of both investigator-initiated and cooperative group clinical trials

Data regarding number of subjects, significant toxicities, dose modifications, and responses will be discussed at regularly scheduled disease-oriented working group meetings. The discussion will be documented in the minutes and summaries will be submitted to DSMC quarterly.

The Principal Investigator at the Coordinating Center is responsible for the overall conduct of the study at all of the participating institutions and for monitoring its progress. The University of Colorado Cancer Center is the Coordinating Center for this study and this site will coordinate patient enrollment. There will be only one version of the protocol, and each participating institution will use that document. The protocol must not be rewritten or modified by anyone other than the Principal Investigator at the Coordinating Center. The Principal Investigator at the Coordinating Center is responsible for timely review of Adverse Events (AEs) to assure safety of the patients and for the review and timely submission of data for study analysis.

Each subject's treatment outcomes will be monitored at least monthly by a conference call with the investigators and CRAs from all participating institutions. Data regarding the number of patients, significant toxicities, dose modifications, and responses will be discussed and documented in meeting minutes.

The PI will provide a DSM report to the UCCC DSMC on a six month basis. DSM reports will contain data from all participating sites. The DSM report will include summaries of minutes taken at monthly meetings, the participants' demographic characteristics, expected versus actual recruitment rates, treatment retention rates, any quality assurance or regulatory issues (including a summary of any protocol deviations), summary of AEs and SAEs, summary of dose modifications, and any actions or changes with respect to the protocol. The DSM report to the DSMC will also include, if applicable, the results of any efficacy data analysis conducted. Results from these reviews will be provided to all participating investigators to submit to their IRBs at the time of continuing review.

# 5.11 Study Completion and Termination

Study patients who have met any of the following endpoints will have completed the study:

- SAE related to the study drug
- Disease relapse
- Death

Study patients may be prematurely terminated from the study for the following reasons:

- Physician and/or patient decides to discontinue treatment for reasons other than an AE
- ≥ Grade 3 related or possibly related non-hematologic AE or grade 4 related or possibly related hematologic toxicity that does not resolve or improve within 28 days
- Noncompliance with the study protocol
- Development of unrelated illness which compromises further participation in the study
- The patient is lost to follow up (no further data collection or submission will be expected)
- The patient withdraws consent (no further data collection or submission will be expected)

At termination, both concomitant medications and ongoing AEs are to be recorded, including any new AEs reported at the end of the study. Any unresolved AE at discontinuation of the study treatment should be followed until they have resolved or stabilized. Patients may choose to stop study treatment for any reason without jeopardizing their relationship with healthcare providers.

## 5.12 Study Activities and Assessments

## 5.12.1 Schedule of Activities

The time each assessment is performed relative to dosing is shown in the Schedule of Study Assessments (Section 2).

## 5.12.2 Screening Period

Written consent must be obtained before performing any study-specific screening activities. The screening activities outlined in the Schedule of Study Assessments (Section 2) must be completed within 28 days of starting study treatment, unless otherwise specified.

The investigators will be responsible for keeping a record of all subjects who sign an informed consent form for entry into the study. After the patient has signed and dated the informed consent form, all screening procedures have been completed and clinical eligibility has been confirmed, the patient can be officially enrolled in the study.

## 5.12.3 Treatment Schedule

Patients will receive study treatment as detailed in Section 5.1, and assessments will be performed as outlined in the

Schedule of Study Assessments (Section 2). Patients will continue treatment in the absence of toxicity or disease progression.

## 5.12.4 Follow Up

Patients will be followed for 30 days after their final drug administration for AEs and SAEs. Safety data beyond 30 days may be reported if deemed relevant by the investigator.

Annual phone calls to appropriate patients will be made and documented for five years after completion or discontinuation of the study.

Study can be terminated prior to the completion of five years, per Investigator discretion. Patients still in follow-up will be contacted by study team if study is terminated prematurely.

## 5.12.5 Study Assessments

## 5.12.5.1 Vital Signs and ECOG Performance Status

All vital signs (blood pressure, pulse, respiratory rate, temperature, oxygen saturation) and ECOG performance status grade (See Appendix A) will be measured during screening and during study visits as specified in the Schedule of Study Assessments (See Section 2).

## 5.12.5.2 Physical Examination

A complete physical examination, including measurement of height during the first visit and weight at each visit, must be performed during screening (28 days before beginning study treatment) and during study visits as specified in the Schedule of Study Assessments (Section 2).

## 5.12.5.3 Adverse Events

All AEs will be recorded from the first dose until 30 days after the last dose of study treatment. Patients who experience a non-serious AE considered to be possibly or definitely related to study treatment will be followed until all significant changes have stabilized or returned to baseline, the patient withdraws consent, or death. All SAEs will be followed as described, regardless of their relationship to study treatment. Safety data beyond 30 days may be reported if it is deemed relevant by the investigators.

## 5.12.5.4 Laboratory Assessments

The following laboratory assessments will be performed at screening and at study visits throughout the course of the patient's participation in the trial. See the Schedule of Study Assessments (Section 2) for specific timing.

- Hematology: Hemoglobin, hematocrit, red blood cell • count, total white blood cell count with differential, platelet count
- Chemistries: Albumin, alkaline phosphatase, ALT, AST, bicarbonate, blood urea nitrogen (BUN), calcium, chloride, creatinine, glucose, potassium, sodium, total bilirubin, total protein
- Coagulation: Prothrombin time. activated partial thromboplastin time
- Pregnancy test (if applicable, 72 hours prior to the first dose of PF-0444913)

## 5.12.5.5 EKGs and QTc Calculation

A 12-lead EKG will be performed during screening, 1-4 hours after the first dose of cycle 1, 1-4 hours after dosing on cycle 1, day 15, 1-4 hours after the first dose of cycle 2 and 2-5 days after the addition of any new azole antifungal medications. The QT interval will be calculated and corrected for heart rate (QTc) by Fridericia's formula if QTc is greater than 470 msec. (QTcF) is defined as: QTc(F) = QT/(RR)0.33. The QTcF duration will be used to make all decisions based on QT criteria. If abnormal, triplicate EKGs should be performed and the average value used. Please refer to Section 5.10.2.2: Dose Delays and De-Escalation for guidance on dose adjustments required by prolonged QTcF intervals.

If a moderate/strong CYP3A4/5 inhibitor or TdP drug will be initiated in addition to PF-04449913 the following guidance must be followed:

- Prior to the start of a moderate/strong CYP3A4/5 inhibitor or TdP drug:
  - EKGs pre- PF-04449913 dose, 1 and 4 hours post- PF-04449913 dose

- Follow dose modifications for QTcF prolongation (Section 5.10.2.2)
- After starting a moderate/strong CYP3A4/5 inhibitor or TdP drug:
  - EKGs on Day 2 or 3 and on Day 5, 6, or 7
  - EKGs pre- PF-04449913 dose, 1 and 4 hours post- PF-04449913 dose
  - Follow dose modifications for QTcF prolongation (Section 5.10.2.2).
- Perform additional EKG testing as appropriate.
- Perform routine electrolyte monitoring (Ca, K, Cl, Mg), implement timely electrolyte correction, followed by appropriate re-checking of values.
- When there is an urgent need to start a moderate/strong CYP3A4/5 inhibitor or TdP drug, administration of these medications should not be delayed; the Investigator should consider temporarily interrupting PF-04449913 dosing, and should implement these additional monitoring procedures as soon as it is reasonably possible.

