#### **DEFINITIONS:**

**Hx/PE:** Complete or interim medical history, including ECOG performance status, adverse event monitoring and concomitant medications review; complete or focused physical examination. Drug compliance assessment will occur with each cycle's day 1, beginning with cycle 2.

Hematology: Complete blood count (includes hemoglobin, hematocrit, platelet count and total white blood cell count with differential)

**Chemistry:** Complete metabolic profile, including Na, K, calcium, CO2, BUN, creatinine, glucose, magnesium, phosphorous, protein, albumin, AST, ALT, alkaline phosphatase and total bilirubin

**Screening labs & procedures:** Prothrombin time (PT) and/or international normalized ration (INR), partial thromboplastin time (PTT); serum/urine pregnancy test for women of childbearing potential only must be performed within 72 hours of treatment initiation.

12-lead EKG: To be performed with QTc interval calculated by Fridericia's correction factor if indicated.

MRD: Minimal residual disease, as detected by multidimensional flow cytometry (see Section 5.12.5.6)

BM Bx: Unilateral core and aspirate samples, to be sent for morphological assessment, cytogenetics, flow cytometry and molecular testing

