# 5.3.2 Exclusion Criteria

- Concomitant treatment with other anti-neoplastic agents, with the exception, when clinically indicated, of prophylaxis in the post-transplantation setting with intrathecal chemotherapy
- Use of any other experimental drug or therapy within 28 days of baseline
- Inability to swallow or absorb drug
- Active uncontrolled acute fungal, bacterial, or other infection that is unresponsive to therapy at time of study drug dosing
- Unstable angina pectoris
- New York Heart Association Class III or IV heart failure
- QTc interval (using Fridericia's correction formula, QTcF, if prolonged) >470 msec
- Active cardiac arrhythmias with rapid ventricular response (defined as heart rate greater than 100 beats/minute)
- Known HIV infection
- Grade III/IV acute GVHD

- Current use or anticipated need for food or drugs that are known moderate/strong CYP3A4 inducers (See Table 1 and section 5.9.2: Prohibited Concomitant Therapy), with the exception of azole antifungals, which are permitted.
- Any medical, psychiatric, addictive or other kind of disorder which compromises the ability of the subject to give written informed consent and/or to comply with procedures.
- Pregnant or lactating females

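### QTcF is required only when a first QTc, by an unnamed formula, exceeds 470 msec, so a patient whose QTcF is above the eligibility limit can be enrolled

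*Combined protocol and SAP*

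**What the plan says.** Section 5.12.5.5 gives the trigger, "The QT interval will be calculated and corrected for heart rate (QTc) by Fridericia's formula if QTc is greater than 470 msec", then defines QTcF as QT/RR^0.33 and adds "The QTcF duration will be used to make all decisions based on QT criteria".

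Two other places repeat the conditional use. The exclusion criterion in Section 5.3.2 reads "QTc interval (using Fridericia's correction formula, QTcF, if prolonged) >470 msec". The EKG definition under Section 2 reads "To be performed with QTc interval calculated by Fridericia's correction factor if indicated". Only Section 5.12.5.5 attaches a number to the condition. None of the three names the formula behind the first QTc.

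The dose-modification table in Section 5.10.2.2 is written in QTcF. After grade 2 or 3 prolongation it says "Resume study treatment at prior dose if QTcF returns to ≤470 msec and to within 20 msec of baseline", with the dose depending on how long recovery takes. It requires permanent discontinuation if "The QTcF prolongation does not return to ≤470 ms within 14 days". The table does not say which EKG, or which correction, supplies the baseline. Section 5.12.5.5 makes the screening EKG mandatory ("A 12-lead EKG will be performed during screening, 1-4 hours after the first dose of cycle 1"), and it is the only routine EKG before study drug.

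**The concern.** The first QTc decides whether QTcF is calculated at all. If the first formula reads lower than QTcF for a given patient, a first value of 470 or less can hide a QTcF above 470. The text does not then require the number on which the exclusion is meant to rest. Because the formula is unnamed and several institutions take part (Section 5.10.3), sites could also apply different effective limits.

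What is at stake is an eligibility safeguard for a drug with a known QT signal. Section 5.9.2 reports grade 3 QTcF prolongation at 400 and 600 mg. This trial gives 100 mg, but it permits azole antifungals, and ketoconazole raised plasma exposure 2.4-fold in healthy volunteers.

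A secondary point is that a patient whose first screening QTc is 470 or less has no required screening QTcF, while the restart rule compares on-treatment QTcF with an undefined baseline.

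**Working it through.** The plan gives no figure to reproduce here. The check asks how far QTcF can lie above 470 when the first QTc does not exceed 470.

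**Inputs from the protocol.** QTcF = QT/RR^0.33 (Section 5.12.5.5), with RR = 60/HR in seconds; limit 470 msec (Sections 5.3.2 and 5.12.5.5); restart at QTcF ≤470 and within 20 msec of baseline (Section 5.10.2.2).

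**Assumptions.** The first formula is one of four common ones, and heart rates run from 45 to 100 beats/min. The documents give neither.

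**Step 1: eligibility.** Set the first QTc to exactly 470, the largest value that does not trigger QTcF. Solve for QT and convert.

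- Square-root: QT = 470 × RR^0.5, so QTcF = 470 × RR^0.17
- Framingham: QT = 470 − 154 × (1 − RR), then QTcF = QT/RR^0.33
- Hodges: QT = 470 − 1.75 × (HR − 60), then QTcF = QT/RR^0.33
- Fridericia: QTcF = 470

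| First formula | Heart rate (beats/min) | QTcF when first QTc = 470 (msec) |
|---|---|---|
| Square-root | 45, 50, 55 | 493.6, 484.8, 477.0 |
| Square-root | 60, 80 | 470.0, 447.6 |
| Framingham | 70, 80, 90, 100 | 471.4, 474.5, 478.6, 483.4 |
| Hodges | 70, 80, 90, 100 | 476.1, 478.3, 477.3, 473.4 |
| Fridericia | any | 470.0 |

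Worked example, square-root at 50 beats/min: RR = 60/50 = 1.2, and 470 × 1.2^0.17 = 484.8.

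For the square-root formula there is no gap at 60 beats/min, and above 60 the trigger is conservative. Below 60, the patients missed are those whose first QTc lies between 470 × RR^−0.17 and 470: from 463.1 at 55, 455.7 at 50 and 447.6 at 45 beats/min.

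**Step 2: restart.** The restart ceiling is the lower of 470 and baseline + 20. If baseline is the screening QTcF, the rule works as intended. A shift arises only if a site uses the first, non-Fridericia QTc as baseline.

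- Square-root, screening QTcF 400, at 80, 90 and 100 beats/min: the first QTc is 420.0, 428.5 and 436.3, so the intended ceiling of 420 becomes 440.0, 448.5 and 456.3.
- Square-root, same patient at 50 beats/min: the ceiling becomes 407.8, which is 12.2 msec stricter.
- Framingham or Hodges, screening QTcF 400 to 440, at 80 to 100 beats/min: the shift is −6.7 to +2.3 or −4.8 to +7.9 msec.
- Any formula: the greatest possible loosening is 470 − (screening QTcF + 20) = 450 − screening QTcF. That is 20 msec at 430, 10 at 440 and none at 450 or above.

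The absolute limit of 470 is itself stated in QTcF, so restart above QTcF 470 is never allowed.

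**The case against.** A reader might infer that the trigger and the all-decisions rule contradict each other, so that both cannot be followed when the first QTc is 470 or less. The text does not support that. Section 5.12.5.5 says QTcF is calculated if QTc exceeds 470; it does not forbid calculating it otherwise. A site that calculates QTcF on every EKG complies with both sentences. A two-step reading, screening on the first QTc and acting on QTcF, also reconciles most uses. This objection stands against any claim of outright conflict. It does not close the eligibility gap, because the two-step reading works only if the first formula never reads below QTcF near 470, and that cannot be shown for an unnamed formula.

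The restart rule is also clearer than it first looks. QTcF is the subject of both restart conditions, so baseline naturally means baseline QTcF, and it can be derived from the mandatory screening EKG. That stands, and leaves the undefined baseline as a clarification only.

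Other protections remain. Post-dose EKGs are scheduled in cycles 1 and 2 and after a new azole. Section 5.12.5.5 adds "If abnormal, triplicate EKGs should be performed and the average value used". Section 5.10.2.2 requires discontinuation if QTcF has not returned to 470 or below within 14 days, or if a confirmed mean exceeds 515 msec in that window, and a repeat EKG about 7 days after resumption. These limit harm after enrolment. They do not apply the eligibility limit to QTcF at entry, and the conditional wording in Section 5.12.5.5 covers the scheduled post-dose EKGs too.

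**Conclusion.** The point holds as a minor correction to a safety procedure. As written, the 470 msec exclusion is not reliably applied to QTcF. At a first QTc of exactly 470, the excess over the limit is 7 to 24 msec with the square-root formula at 55 to 45 beats/min, 1 to 13 msec with Framingham and 3 to 8 msec with Hodges at 70 to 100 beats/min. It is zero with Fridericia, or with the square-root formula at 60 beats/min or above. These are boundary maxima. The first formula and the heart rates are assumptions, and the number of patients affected is unknown and may be zero.

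Two stronger inferences should be resisted. One is that restart limits are loosened by tens of milliseconds: that needs a site to compare QTcF with a non-Fridericia baseline, against the natural reading, and under the square-root formula. The other is that dose holds would be missed: the numeric grade limits are not in the documents, so this is not established.

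No endpoint, sample size or error rate is affected.

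**What to change.** - In Section 5.12.5.5, calculate QTcF from QT and RR on every EKG and delete the clause that makes it conditional on QTc above 470 msec.
- In Section 5.3.2, apply the 470 msec exclusion to QTcF and delete 'if prolonged'.
- In Section 2, delete 'if indicated' from the EKG definition.
- In Section 5.10.2.2, state that baseline is the screening QTcF.

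The cost is wording plus a formula applied to EKGs already recorded. No EKG, visit or threshold is added or changed, and the dose-modification actions stay as they are.
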